### 1. PROTOCOL SYNOPSIS

Title	Clinical metagenomic next-generation sequencing for diagnosis of meningitis and encephalitis – the PDAID trial
Short Title	Precision Diagnosis of Acute Infectious Diseases – PDAID
Objectives	To compare the performance of a clinically validated metagenomic next-generation sequencing (mNGS) assay with conventional microbiological testing in diagnosis of infectious causes of meningitis and encephalitis in acutely ill hospitalized patients
Design	Single-group, multisite, prospective clinical diagnostic trial.
Outcomes	
Primary
 

1. Clinical mNGS assay performance (sensitivity, specificity, positive predictive value, negative predictive value)

2. Number and proportion of infectious diagnoses made using the mNGS assay

 
Secondary
 

1. Impact of mNGS results (positive and negative) on clinical reasoning

2. Impact of mNGS results (positive) on clinical management and outcomes

3. Potential clinical utility of communicating results from supplementary mNGS analyses to physicians

4. Feasibility of a clinical microbial sequencing board (CMSB) for discussing and interpreting mNGS results in clinical context

Interventions	

1. Running an mNGS assay for pathogen detection from cerebrospinal fluid (CSF) in a CLIA (Clinical Laboratory Improvement Amendments)-certified laboratory.

2. Reporting mNGS results in the patient electronic medical record

3. Discussing mNGS results with primary care providers and associated consulting physicians during weekly CMSB meetings

Sample Size 300  
Population Pediatric and adult patients with meningitis, encephalitis, and/or myelitis

Eligibility  
Criteria

Inclusion Criteria
Age: Any
Hospital admission or transfer with clinical syndrome of meningitis, encephalitis or myelitis
Symptom onset (or exacerbation) within 2 weeks of CSF sampling
Lack of an etiologic diagnosis at time of enrollment
Meningitis
Fever $\geq 38^{\circ}\text{C}$ *
AND:
Abnormal neuroimaging or CSF WBC count $\geq 5/\text{cubic mm}$ *
With or Without:
stiff neck, headache or seizure
Encephalitis
Major Criterion:
Altered mental status lasting $\geq 24$ h with no alternative cause identified
Minor Criteria (at least 2 required):
Fever $\geq 38^{\circ}\text{C}$ *
Seizures not fully attributable to a preexisting seizure disorder

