Over the course of the Precision Diagnosis of Acute Infectious Diseases demonstration project,, each case is discussed with a team of leading experts in neurology, infectious disease and microbiology (CMSB, “clinical microbial sequencing board”). The mNGS findings are put into clinical context, and appropriate treatment and management decisions are recommended to treating physicians. This helps to ensure that proper management decisions are made and that the assay results are interpreted according to the clinical context, thus mitigating risk that may be associated with diagnostics provided outside of the healthcare system associated with the patient.

During the demonstration project, positive findings by mNGS are evaluated using orthogonal testing (clinical testing is preferred if available, or research-based PCR confirmatory testing) to assess the possibility of false-positive results. However, as this assay utilizes significant advances in pathogen detection technology, there is the potential to detect the presence of a pathogen that may not yet be detectable via other diagnostic assays (i.e. detecting a virus before antibody production).

Potential false-negative mNGS results (negative mNGS assay but positive by conventional testing) are also reviewed with additional discrepancy testing performed, as necessary.

The results of the mNGS assay do not solely determine the need for therapy or other patient interventions. Conventional test results and mNGS results are used in the proper clinical context to guide therapy decisions. Given the overall mNGS test performance during clinical laboratory validation studies, expert review and case discussion, and the use of discrepancy testing as needed, the mNGS assay (device) as performed poses a non-significant risk to patients.

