### 6.2. Final Statistical Analysis Plan

This was a one-year, multicenter, prospective cohort study in which subjects were enrolled based on a particular exposure (i.e. idiopathic meningitis +/- encephalitis and/or myelitis) and then followed over time to assess for the occurrence of the outcome (i.e. results of CSF mNGS testing). Prospective enrollees were identified by physician referral, computerized provider order entry, patient chart review, or screening of daily EMR reports (Supplementary Appendix). Given funding and clinical testing capacity constraints, sample size estimates (n=300) were based on convenience without formal statistical considerations. The target condition was idiopathic meningitis, encephalitis, and/or myelitis in patients undiagnosed at time of enrollment. The index test was the CSF mNGS assay, and the reference standard was a composite of conventional testing and orthogonal confirmatory testing of mNGS-only positive results, either with respect to all clinical testing or direct detection (i.e. non-serologic) testing of CSF only.

As gold standard reference results for diagnosis of meningitis and encephalitis was not available (due to the varying extent of diagnostic testing done at each hospital, lack of detailed performance characteristics for each test performed locally, and lack of availability of comprehensive gold standard testing for meningitis and encephalitis), obtaining unbiased estimates of sensitivity and specificity was not possible. Thus, the comparative performance measures of mNGS relative to conventional testing are reported as positive percent agreement (PPA) and negative percent agreement (NPA) to the composite reference standard, in accordance with statistical guidance from the FDA. PPA and NPA were calculated

using standard formulas for proportions, and 95% confidence intervals for these proportions were determined using Wilson's method.

The primary analysis was a comparison of the performance of the mNGS assay versus conventional (direct detection) testing using the composite results of direct detection testing of CSF, including orthogonally confirmed mNGS results. Secondary analyses included 2x2 contingency analyses of the PPA and NPA of the mNGS assay relative to other combinations of conventional diagnostic testing including serology and test results from other tissue types.

The final statistical analysis plan may also be viewed as part of the final IRB protocol on page 78.

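### The primary composite counts confirmed mNGS-only positives as reference positives, and SAP 6.2 does not clearly call for the unresolved 2x2 table beside it

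*Combined protocol and SAP*

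**What the plan says.** Section 6.2 states that "the reference standard was a composite of conventional testing and orthogonal confirmatory testing of mNGS-only positive results", taken either over all clinical testing or over direct-detection CSF testing only. The primary analysis takes the CSF version, "using the composite results of direct detection testing of CSF, including orthogonally confirmed mNGS results". Results are "reported as positive percent agreement (PPA) and negative percent agreement (NPA) to the composite reference standard", with Wilson 95% intervals, and 6.2 introduces them as measures of mNGS against conventional testing. The secondary 2x2 analyses take mNGS "relative to other combinations of conventional diagnostic testing including serology and test results from other tissue types".

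The Synopsis gives the objective: "To compare the performance of a clinically validated metagenomic next-generation sequencing (mNGS) assay with conventional microbiological testing".

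Section 9.4 of the final protocol (version 1.16) says that positive mNGS findings go to orthogonal testing, preferably by a clinical test and otherwise by research PCR. It warns that "there is the potential to detect the presence of a pathogen that may not yet be detectable via other diagnostic assays". For the other discordant group it says: "Potential false-negative mNGS results (negative mNGS assay but positive by conventional testing) are also reviewed with additional discrepancy testing performed, as necessary". Neither 6.2 nor 9.4 says that such a review can take a conventional positive out of the reference.

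The original SAP (6.1) used the same composite. The change recorded in 6.3 replaced sensitivity and specificity with PPA and NPA and left the reference as it was.

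**The concern.** In the reference as 6.2 defines it, only one discordant group can change status. An mNGS-only positive that is confirmed becomes a reference positive, and so an agreement for mNGS. A conventional-only positive stays a reference positive whatever its discrepancy testing shows. Agreement with the composite is thus a mixture of agreement with conventional CSF testing and the effect of moving confirmed index-test results into the reference. The stated objective is a comparison with conventional testing, so a reader needs to see both parts.

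The named secondary tables widen the conventional side to serology and other tissues. They do not clearly include the plain table of mNGS against conventional direct-detection CSF results. Nor does 6.2 ask how many discordant results were confirmed, refuted or could not be tested.

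**Working it through.** There is no figure in the plan to reproduce. The sample size of 300 is described as a convenience figure, and no 2x2 counts are given. The direction can be settled by algebra. The size can only be illustrated.

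**Notation.** a = both positive; b = conventional only; c = mNGS only; d = both negative; x = mNGS-only positives confirmed. Under the default that 6.2 implies, conventional-only results stay reference-positive and unconfirmed mNGS-only results are reference-negative.

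**Formulas.**
- Unresolved: PPA = a/(a+b); NPA = d/(c+d).
- Composite: PPA = (a+x)/(a+b+x); NPA = d/(c+d−x).
- Shift in PPA = bx/[(a+b)(a+b+x)]; shift in NPA = dx/[(c+d)(c+d−x)]. Neither can be negative.
- Conventional testing against the composite: PPA = (a+b)/(a+b+x); NPA = (c+d−x)/(c+d−x) = 100%.

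**Illustration (all cells assumed): a/b/c/d = 30/20/20/230, n = 300.**

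| x | mNGS PPA (Wilson 95%) | mNGS NPA (Wilson 95%) | Conventional PPA |
|---|---|---|---|
| 0 (unresolved) | 30/50 = 60.0% (46.2–72.4) | 230/250 = 92.0% (88.0–94.8) | 100% |
| 5 | 35/55 = 63.6% (50.4–75.1) | 230/245 = 93.9% (90.1–96.3) | 90.9% |
| 10 | 40/60 = 66.7% (54.1–77.3) | 230/240 = 95.8% (92.5–97.7) | 83.3% |
| 15 | 45/65 = 69.2% (57.2–79.1) | 230/235 = 97.9% (95.1–99.1) | 76.9% |
| 20 | 50/70 = 71.4% (59.9–80.7) | 230/230 = 100% (98.4–100) | 71.4% |

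Check at x = 15: PPA shift 20·15/(50·65) = 9.2 points; NPA shift 230·15/(250·235) = 5.9 points.

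**Range over assumed tables.**
- With a = 20–40, b = 10–30, c = 10–30, n = 300 and 50–100% of mNGS-only results confirmed, PPA rises 1.8 to 22.5 points, NPA rises 1.8 to 13.0 points, and conventional PPA falls 6.7 to 50.0 points. The largest PPA rise is at a = 20, b = 30, x = 30: 30·30/(50·80) = 22.5 points.
- The 1.8-point lower end for PPA comes from that choice of cells. With a = 43 and b = 7 (PPA 86.0%, close to the 86.1% validation sensitivity in section 9.4, which is itself a post-discrepancy figure), x = 2 gives 7·2/(50·52) = 0.5 points and x = 3 gives 7·3/(50·53) = 0.8 points.

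**What the mNGS composite row alone leaves open.** Results of 40/60 and 230/240 fit x = 0 with cells 40/20/10/230 (unresolved PPA 66.7%, NPA 95.8%). They fit x = 20 with cells 20/20/30/230 equally well (unresolved PPA 20/40 = 50.0%, NPA 230/260 = 88.5%).

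**Untestable mNGS-only results.** Take the 30/20/20/230 table with 10 confirmed, 5 refuted and 5 untestable. The implied default gives PPA 40/60 = 66.7% and NPA 230/240 = 95.8%. Counting the 5 as reference-positive gives 45/65 = 69.2% (57.2–79.1) and 230/235 = 97.9% (95.1–99.1).

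**The case against.** **The composite is disclosed.** This stands. Section 6.2 says that confirmed mNGS results are included, names the composite as the comparator and explains why unbiased sensitivity and specificity could not be had. Disclosure does not show the size of the shift.

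**The table could be rebuilt.** A reader might infer that the effect of resolution cannot be separated at all. That goes too far. If the composite results for both tests are shown with counts, x is the number of reference positives minus the number of conventional positives. In the x = 10 case, 60 − 50 = 10, so a = 40 − 10 = 30, b = 20, c = 10 + 10 = 20 and d = 230. What remains is that 6.2 does not require those counts.

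**The asymmetry also works against mNGS.** A reader might infer that the composite favours mNGS overall, or overstates its true specificity. The documents do not support either reading. In the x = 10 case, removing 5 refuted conventional-only positives would raise mNGS PPA from 66.7% to 40/55 = 72.7%, and NPA from 95.8% to 235/245 = 95.9%. The 100% conventional NPA also favours the comparator. The result here concerns agreement only; the effect on true specificity has no known sign.

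**The secondary analyses may already cover it.** The wording is open-ended and could be read to include the unresolved CSF table. Its examples are wider sets of tests, however, so the table is not clearly called for.

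**Conclusion.** The point holds as a low-cost reporting improvement. It does not show that the primary analysis is invalid. As 6.2 is written, mNGS PPA and NPA against the composite can only equal or exceed agreement with conventional direct-detection CSF testing. That direction rests on the implied default set out in the working and needs no assumed numbers. The size in this trial cannot be derived from the documents. Under assumed tables the PPA rise runs from about half a point to 22.5 points, and it is large only when mNGS misses many conventional positives and many mNGS-only results are confirmed.

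**What to change.** Keep the composite as the primary analysis and add to 6.2:

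1. The unresolved 2x2 of mNGS against conventional direct-detection CSF testing, with PPA, NPA and Wilson intervals. Leave out tests known to have been run to confirm an mNGS result, where the record shows this. Section 9.4 prefers clinical tests for confirmation, so such tests could otherwise be counted as conventional.
2. The number of mNGS-only positives, and of conventional-only positives sent for discrepancy testing, that were confirmed, not confirmed or not testable.
3. A sensitivity analysis that classes untestable mNGS-only positives as reference-positive instead of the implied reference-negative.

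The cost is SAP wording, one supplementary table and a tally, mostly from results already needed to build the composite. Identifying confirmatory tests may need some record review. Less favourable PPA and NPA may appear beside the composite figures. The unresolved NPA also counts true infections found only by mNGS as disagreements, so neither table should stand alone.

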### 6.3. Summary of Changes to the Statistical Analysis Plan

In the Institutional Review Board (IRB)-approved protocol titled "Study Protocol for the PDAID Trial", clinical trials registration number NCT02910037, one of the primary outcomes is described as an assessment of clinical mNGS assay performance (sensitivity, specificity, positive predictive value, and negative predictive value). These performance measures are also mentioned in the document as an explanation for why the use of the device in the study (the clinical mNGS assay) poses a non-significant risk.

During the course of peer review, it was brought up that obtaining unbiased estimates of sensitivity and specificity was not possible as gold standard reference results for diagnosis of meningitis and encephalitis were not available. Thus, the comparative performance measures of mNGS relative to conventional testing are calculated and reported in the paper as positive percent agreement (PPA) and negative percent agreement (NPA) to the composite reference standard, in accordance with statistical guidance from the FDA ("Statistical Guidance on Reporting Results from Studies Evaluating Diagnostic Tests – Guidance for Industry and FDA Staff", Food and Drug Administration, U.S. Department of Health and Human Services, issued March 13\*, 2007).

## 7. APPENDIX

### 7.1. Enrollment Flow Chart
